Following direct laryngoscopy, the catheter will be introduced orally and inserted through the vocal cords into the trachea to the desired depth of 1-2 cm, the laryngoscope will be carefully removed while the catheter is secured by the fingers of the neonatologist/investigator, who will finally close the neonate's mouth. The correct position of the catheter into the trachea will be confirmed by the visualization of tip depth markings and by the tip-to-lip measurement. The thin catheter presents three different ring markings close to the tip, equal to 1, 2 and 3 cm ([Figure 1C](#)) and helpful to address the depth of insertion beyond the vocal cords. Moreover, the catheter presents markings going from 5 to 9 cm for the tip-to-lip measurement, which represents the standard method to estimate the correct position also of the ETT [\[23\]](#).

After having confirmed the correct position of the catheter into the trachea, the syringe filled with poractant alfa suspension will be connected to the Luer of the catheter and poractant alfa will be instilled over 0.5-3 minutes with careful observation of the neonate's continuous spontaneous breathing. Once the surfactant is administered, the catheter will be removed. Before removing the LISA catheter, it should be fully cleared of surfactant with some additional air. After completion of surfactant administration, ventilatory support may require transient adjustments. Airways suction should not be performed for 1 hour after surfactant instillation, unless signs of significant airway obstruction occur.

If on the first attempt the catheterization of the trachea is not possible within 30 seconds, the laryngoscope should be removed and if required neonate's recovery allowed. Then a second

attempt should be performed for a total number of 3 attempts.

Details of the procedure as well as neonate's vital signs and any occurring adverse event will be recorded according to the time points of the protocol by the team member assisting or observing the procedure.

Figure 1: CHF 6440

Figure 1A
CHF 6440 Full View

Figure 1B
Close-up on CHF 6440 Components

a) Standard Luer

b) Rounded and Soft Tip

[figure not shown]

Figure 1C
Close-up of Markings Present on CHF 6440 Shaft

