6.2.3.5 Need for resuscitation during surfactant administration

In both arms of the study, if a life-threatening event requiring resuscitation occurs during poractant alfa administration, the procedure of surfactant administration will be stopped and resuscitation provided starting from supplying Positive Pressure Ventilation (PPV) and following step-by-step the American Guidelines for Neonatal Resuscitation [[24,25](#)].

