8. EFFICACY ASSESSMENTS

The following variables will be used to describe the efficacy of the two procedures:

- Percentage of neonates needing invasive mechanical ventilation (MV) in the first 72 hours of life, 28 days PNA and within 36 weeks PMA defined as follows:

ETT group

- neonates not extubated within 1 hour from initial surfactant administration and receiving MV for more than 1 hour;
- neonates extubated and re-intubated to receive MV of any duration.

LISA group

- neonates intubated to receive MV of any duration,
 - Duration of invasive ventilation (hours) in the first 72 hours of life, 28 days PNA and within 36 weeks PMA;
 - Percentage of neonates needing any intubation procedure, outside the initial surfactant administration period, in the first 72 hours of life, in the first 28 days PNA and within 36 weeks PMA;
 - SpO₂ at time 0 (study treatment administration), 5, 15, 30 minutes, at 1, 6, 12, 24, 48, 72 and 120 hours post treatment; additionally, at 28 days PNA and at 36 weeks PMA for neonates still receiving any form of respiratory support;
 - FiO₂ at time 0 (study treatment administration), 5, 15, 30 minutes, at 1, 6, 12, 24, 48, 72 and 120 hours post treatment; additionally, at 28 days PNA and at 36 weeks PMA for neonates still receiving any form of respiratory

support;

- SpO₂/FiO₂ at time 0 (study treatment administration), 5, 15, 30 minutes, at 1, 6, 12, 24, 48, 72 and 120 hours post treatment; additionally, at 28 days PNA and at 36 weeks PMA for neonates still receiving any form of respiratory support;
- Percentage of neonates needing additional surfactant doses and number of surfactant doses;
- Duration of oxygen alone supplementation (days) and any non-invasive ventilation during the study (days);
- Blood gas analysis, specifically acid-base balance parameters (i.e. pH, pCO₂, pO₂, HCO₃, BE, lactate) pre-surfactant administration (when applicable), at 1 hour, 6 hours, 24, 48 and 72 hours after study treatment.

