For pharmacovigilance purposes, all SAEs should be followed-up in order to elucidate as completely and practically as possible their nature and/or causality until resolution of all queries, clinical recovery is complete, laboratory results have returned to normal, stable condition is reached or until the subject is lost to follow-up. Follow-up may therefore continue after the subject has left the study. In this case, the follow-up will continue with no timelines for related SAEs, while for unrelated SAEs the type and extent of follow-up undertaken will be determined for each individual case and will depend upon the nature (e.g. events with poor prognosis or which do not resolve), severity and medical significance of the event.

AEs related to the procedure for surfactant administration

The procedure for surfactant administration will last from the application of the laryngoscope up to the removal of the CHF 6440 catheter in the LISA treatment group or the ETT in the comparator arm within one hour after the instillation of poractant alfa.

All AEs during procedures for surfactant administration will be carefully monitored and recorded in both arms. Specific focus will have to be paid on the following AEs:

- Obstruction of the CHF 6440 catheter or ETT;
- Bradycardia;
- Neonatal oxygen desaturation;

- Apnoea;
- Hypotension requiring treatment;
- Any episodes of cough, sneezing, choking, laryngospasm, surfactant reflux, vomiting.

A complete qualitative risk assessment has been conducted to identify and mitigate potential safety risks associated with use of CHF 6440 medical device. The results provide evidence that the benefits of using the device outweigh the residual risks and do not highlight any specific additional risk or safety issue than the ones listed above.

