12.3.4. Efficacy variables

Need for mechanical ventilation/intubation

- Percentage of neonates needing invasive mechanical ventilation in the first 72 hours of life, in the first 28 days PNA and within 36 weeks PMA will be compared between group using the Cochran-Mantel-Haenszel (CMH) test adjusted for gestational age group. The CMH adjusted difference with its 95% CI will be presented. Additional analysis will be performed to explore the impact of use of sedation and/or analgesia.
- Percentage of neonates needing any intubation procedure, outside the initial surfactant administration period, in the first 72 hours of life, 28 days PNA and within 36 weeks PMA will be compared between treatments as need for IMV.

SpO₂

- SpO₂ will be analyzed using a linear mixed model for repeated measures (MMRM) including treatment, time point, treatment by time point interaction, and gestational age group as fixed effects and pre-procedure SpO₂ as covariate. The adjusted means in each treatment group, the adjusted mean difference between treatments and their 95% CIs at each time point and averaged over the first 120 hours post-treatment will be estimated by the model. Time profile plot of mean SpO₂ in the first 120 hours post-administration will be presented by treatment group.
- SpO₂ will be summarized by treatments on neonates still receiving respiratory support at 28±2 PNA and 36 weeks PMA by means of descriptive statistics.

FiO₂

- FiO₂ will be analyzed using a linear MMRM including treatment, time point, treatment by time point interaction, and gestational age group as fixed effects and pre-procedure FiO₂ as covariate. The adjusted means in each treatment group, the adjusted mean difference between treatments and their 95% confidence intervals (CIs) at each time point and averaged over the first 120 hours post-treatment will be estimated by the model. Time profile plot of mean FiO₂ in the 120 hours post-treatment will be presented by treatment group.
- FiO₂ will be summarized by treatments on neonates still receiving respiratory support at 28±2 PNA and 36 weeks PMA by means of descriptive statistics.

SpO₂/FiO₂ ratio

- SpO₂/FiO₂ will be analyzed using a linear MMRM including treatment, time point, treatment by time point interaction, and gestational age group as fixed

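### The any-intubation endpoint exempts an undefined initial surfactant period in both arms, so a LISA neonate converted to a tube for the first dose can be counted as not intubated

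*Protocol*

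**What the plan says.** The endpoint appears four times: under efficacy variables and under statistical methods in the Protocol outline, in Section 8, and in Section 12.3.4. Section 8 gives it as "Percentage of neonates needing any intubation procedure, outside the initial surfactant administration period, in the first 72 hours of life", and then for 28 days and 36 weeks. Section 12.3.4 repeats the exemption and adds that the endpoint "will be compared between treatments as need for IMV", which means a Cochran-Mantel-Haenszel test by gestational-age group with an adjusted difference and 95% CI. None of the four places separates the arms or says when the exempt period begins and ends.

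The endpoint next to it in Section 8, need for invasive mechanical ventilation (MV), does have arm-specific rules. For controls it allows for the assigned tube by using a one-hour limit. For LISA it counts "neonates intubated to receive MV of any duration", with no exempt period.

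Three other provisions bear on the boundary:
- Section 10.8 (adverse events): "The procedure for surfactant administration will last from the application of the laryngoscope up to the removal of the CHF 6440 catheter" in the LISA group. In the comparator it lasts to removal of the tube, within an hour of instillation.
- Section 6.2.3.3: after a failed first catheterisation, a further "attempt should be performed for a total number of 3 attempts". The section does not say what follows a third failure.
- Section 6.2.3.5: if resuscitation is needed during administration, the administration is halted first.

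**The concern.** In the control arm the first tube is the allocated method, so the endpoint has to leave it out. In the LISA arm no intubation is allocated, and Section 1.2 presents avoidance of intubation as the reason for the technique. An exemption shared by both arms therefore removes assigned treatment in one arm and can remove treatment failure in the other.

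The case of interest is a LISA neonate in whom catheterisation fails and whose first dose is then given through an endotracheal tube. In ordinary language that intubation belongs to the initial surfactant administration. The neonate received a dose, so Section 12.2 keeps it in the ITT denominator, but it may contribute no event. What is at stake is a between-arm difference with a CI in which one arm's event count depends on an unstated reading.

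**Working it through.** The Protocol states no rate, effect size or power for this endpoint, so there is no figure to reproduce. The check compares the two readings and then bounds the difference between them.

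**Step 1: the two readings.** The narrow reading borrows the Section 10.8 window. The wide reading lets the period run until the first dose has been given, by whatever route.

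| Neonate | Narrow | Wide |
|---|---|---|
| LISA, catheter abandoned, first dose given by tube | counted | exempt |
| LISA, intubated in resuscitation after administration was stopped | counted | unclear; Section 6.2.3.5 points to counted |
| LISA, intubated after the first dose is complete | counted | counted |
| Control, assigned tube for first dose | exempt | exempt |
| Control, not extubated within 1 hour and still ventilated | no new intubation, not counted | same |

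The readings clearly part in the first row, which is a LISA row.

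**Step 2: do other variables record that neonate?**
- The MV endpoint does, if the tube was placed for ventilation. A tube used only to instil surfactant need not qualify.
- The Section 9 count of procedural adverse events requiring intubation does, if an adverse event was recorded. It counts events, not neonates.
- Section 9 also reports failed first attempts, number of attempts, and manoeuvres discontinued for destabilisation. None of these records conversion to a tube.

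A conversion with neither MV nor an adverse event could therefore be missed by all three intubation-related variables.

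**Step 3: upper bound on the shift.** From Section 12.1, n = 100 LISA and 50 control. Assumed: true rates of 30% (LISA) and 40% (control); a share c of 3 to 10% of LISA neonates converted; none of them intubated again in the endpoint window; no compensating loss in controls.
- Events lost: 100 × 0.03 = 3 to 100 × 0.10 = 10, so the LISA rate falls by 3 to 10 points.
- SE of the difference = √(0.3 × 0.7/100 + 0.4 × 0.6/50) = √(0.0021 + 0.0048) = 0.083.
- Shift in SE units: 0.03/0.083 = 0.36 to 0.10/0.083 = 1.2.

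**Step 4: illustration with no true difference.** Let both arms have the same true rate p, and let the wide reading reduce the LISA rate to p − c. The chance of a significant result favouring LISA (two-sided 5% test, unstratified normal approximation) is Φ[(c − 1.96·SE₀)/SE₁], where SE₀ is pooled and SE₁ unpooled. For p = 0.30 and c = 0.05, the pooled rate is (15 + 25)/150 = 0.267, SE₀ = 0.077 and SE₁ = 0.078, which gives about 0.10.

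| c | p = 20% | p = 30% | p = 40% |
|---|---|---|---|
| 2% | 5.0% | 4.5% | 4.3% |
| 5% | 12.6% | 9.9% | 8.8% |
| 10% | 40.5% | 28.4% | 23.5% |

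The nominal chance in that direction is 2.5%. The 95% half-width of the difference is about 13 to 17 points throughout. On the narrow reading c is counted and this effect disappears.

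**The case against.** The strongest reply is that the only procedure window the Protocol defines ends at catheter removal in the LISA group. Section 9 times the overall procedure the same way, Section 6.2.3.3 has the laryngoscope withdrawn after a failed attempt, and Section 6.2.3.5 stops administration before resuscitation. On those provisions a tube placed afterwards falls outside the period and counts. This stands to a large extent. A reader might infer that every LISA neonate intubated for catheter failure or resuscitation is recorded as never intubated. The documents do not support that, and resuscitation intubations most naturally count. What remains is that Section 10.8 defines a differently named period for adverse-event purposes, and the endpoint neither uses its term nor refers to it.

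Two further inferences also go too far. One is that the endpoint ought to contain the MV endpoint. That fails by Section 8's own control definition: a control neonate left on the ventilator for more than an hour needs MV without any new intubation. The other is that all the error must favour LISA. A loosely drawn period could also exempt an early re-intubation in a control, so the net direction is a tendency and not a certainty.

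It is also fair to say that a statistical analysis plan, not at hand here, could settle the boundary, and that the study is descriptive with no primary efficacy endpoint. However, the Protocol itself writes the same exemption for both arms in four places. The trial is open-label, and Section 12.3 allows the analysis plan to be updated at data review before lock. Which LISA intubations are exempt is better settled before then.

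**Conclusion.** The point holds as a defect of definition. One undefined exemption is applied to two arms that need different rules, and two defensible readings give different LISA event counts. The neonate affected is chiefly the one converted to a tube for the first dose. A bias towards LISA is possible on the wide reading but is not demonstrated.

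The size cannot be known from the Protocol. The figure of 3 to 10 points (0.4 to 1.2 standard errors) is a ceiling. It rests on the wide reading, an assumed conversion rate, assumed event rates, and no later intubation of the same neonates; on the Section 10.8 window it is close to zero. The variable is exploratory and the sample size is unaffected. The correction is worth making because it is cheap and removes a possible one-sided omission.

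**What to change.** In the outline (both places), Section 8 and Section 12.3.4:
- Define the initial surfactant administration period separately for each arm.
- In the control group, limit the exemption to the assigned tube insertion for the first dose.
- In the LISA group, count every endotracheal intubation from first laryngoscope insertion onward, including conversion after failed catheterisation and intubation during resuscitation.
- Tabulate the reason for each LISA intubation.

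The cost is wording. Section 7.1.2 already collects need for intubation with dates and times. The change affects how events are counted and leaves every clinical rule as it is. Its one downside is that the LISA figure may look slightly less favourable.

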9. SAFETY ASSESSMENTS

The following variables will be used to describe the safety of the two procedures:

During procedure for surfactant administration

- Number and percentage of neonates with AEs starting during overall procedure for surfactant administration;
- Number and percentage of neonates with AEs starting during overall procedure for surfactant administration judged related to the procedure;
- Number of AEs occurring during overall procedure for surfactant administration requiring either oxygen alone or an increase in FiO₂ without the need for escalation of invasive or non-invasive ventilator support;
- Number of AEs starting during overall procedure for surfactant administration requiring administration of manual (bag and mask) pressure positive ventilation and related duration of ventilation (non- invasive ventilation);
- Number of AEs starting during overall procedures for surfactant administration requiring endotracheal intubation and related duration of intubation (invasive ventilation);
- Number of AEs starting during overall procedures for surfactant administration requiring circulatory support including administration of crystalloids;
- Number of AEs starting during overall procedures for surfactant administration requiring cardiopulmonary resuscitation including administration of cardiac massage or adrenaline.

After first administration

- Number and percentage of neonates with failed 1st attempt to insert the CHF6440/ETT;
- Number of attempts to the first successful insertion;
- Number of device misallocation (esophageal insertion);
- Number of maneuvers discontinued due to neonate's severe destabilization;
- Duration of the whole procedure (starting from the insertion of laryngoscope up to the removal of the catheter or ETT);
- Duration of surfactant administration (min);
- Heart rate (HR) and respiratory rate (RR) (0, 5, 15 and 30 min, 1 hour, 6 and 12 hours after administration);
- Systolic, diastolic, and mean blood pressure (SBP/DBP/ MBP) (15 and 30 min, 1 hour, 6 and 12 hours after administration);
- Premature Infant Pain Profile (PIPP) score [26] (end of surfactant administration).

During the study

- AEs, including incidence of major neonatal complications of prematurity (listed in [APPENDIX III](#)) and adverse drug reactions (ADRs);
- Blood pressure (SBP, DBP, MBP) at 24, 48, 72, 120 hours post-administration;
- Heart Rate (HR) and respiratory rate (RR), at 24, 48, 72, 120 hours post-administration and 28 PNA, 36 weeks PMA, discharge home or 40 weeks PMA whichever comes first;
- Incidence of BPD at 36 weeks PMA;
- Death/BPD incidence at 36 weeks PMA, defined as the incidence of the neonates who are dead or alive but with a diagnosis of BPD at the time of assessment (i.e. 36 weeks PMA);
- Mortality at Day 28 PNA and 36 weeks PMA;
- Oxygen use (alone and/or during invasive and non-invasive ventilation) at Day 28 PNA and 36 weeks PMA;
- Weight, OFC and length at discharge home or 40 weeks PMA;
- Feeding and hearing status at discharge home or 40 weeks PMA, whichever comes first;
- Incidence of major neonatal morbidities at discharge home or 40 weeks PMA, whichever comes first;
- Neonates needing invasive ventilation or non-invasive respiratory support at discharge home or 40 weeks PMA;
- Neonates needing respiratory medications at discharge home or 40 weeks PMA.

24 months (± 3 months) corrected age

(This stand-alone assessment will be analyzed and reported separately from the main phase)

- Health status questionnaire, including:
 - ✓ Bayley Scales of Infant Development (cognitive and language scores);
 - ✓ Feeding method: spoon, nasogastric tube or gastrostomy;
 - ✓ Cerebral palsy evaluation;
 - ✓ Seizure evaluation;
 - ✓ Vision, hearing and communication evaluation;
 - ✓ Clinical assessment of respiratory conditions and morbidity;
 - ✓ Vital signs (SBP/DBP/MBP, HR, RR);
 - ✓ Growth assessment (Weight, OFC and length).

10. ADVERSE EVENTS REPORTING**10.1. Definitions**

An **Adverse Event** is “any untoward medical occurrence in a subject or clinical trial subject administered a medicinal product and which does not necessarily have a causal relationship with this treatment”.

An adverse event can therefore be any unfavorable and unintended sign (including abnormal laboratory finding), symptom, or disease temporally associated with the use of an investigational product, whether or not considered related to the investigational product.

An **Adverse Drug Reaction** is an “untoward and unintended responses to an investigational medicinal product related to any dose administered”.

All adverse events judged by either the reporting Investigator or the Sponsor as having a reasonable causal relationship to an investigational product qualify as adverse reactions. The expression “reasonable causal relationship” means to convey in general that there are facts (evidence) or arguments meant to suggest a causal relationship.

The definition covers also medication errors and uses outside what is foreseen in the protocol, including misuse and abuse of the product.

A **Serious Adverse Event (SAE)/Serious Adverse Drug Reaction** is any untoward medical occurrence or effect that at any dose falls in one or more of the following categories:

- ***Results in death***

Death is not an adverse event but an outcome. It is the cause of death that should be regarded as the adverse event. The only exception to this rule is “sudden death” where no cause has been established; in this latter instance, “sudden death” should be regarded as the adverse event and “fatal” as its reason for being serious.

- ***Is life-threatening***

Life-threatening refers to an event in which the subject was at risk of death at the time of the event (e.g., aplastic anemia, acute renal failure and anaphylaxis). The term does not refer to an event which hypothetically might have caused death if it were more severe.

- ***Requires hospitalization or prolongation of existing hospitalization***

Hospitalization refers to a situation whereby an AE is associated with unplanned overnight admission into hospital, usually for purpose of investigating and/or treating the AE. Hospitalization for the treatment of a medical condition that occurs on an “elective” or “scheduled” basis or for a pre-existing condition that did not worsen during the study should not necessarily be regarded as an AE. Complications that occur during the hospitalization are AEs. If a complication prolongs hospitalization, the event is an SAE.

Emergency room visits that do not result in a formal admission into hospital should be evaluated for one of the other seriousness criteria (e.g., life-threatening; persistent or significant disability or incapacity; medically significant).

- ***Results in persistent or significant disability or incapacity***

The term significant disability should be viewed as any situation whereby an AE has a clinically important effect on the subject’s physical or psychological well-being to the extent that the subject is unable to function normally.

- ***Is a congenital anomaly or birth defect (not applicable for this study)***

- ***Is a medically significant adverse event***

This criterion allows for any situations in which important adverse events/reactions that are not immediately life-threatening or do not result in death or hospitalization may jeopardize the subject’s health or may require intervention to prevent one of the above outcomes.

Examples of such events are: intensive treatment in an emergency room or at home for allergic bronchospasm; blood dyscrasias or convulsions that do not result in hospitalization; or development of drug dependency or drug abuse.

Medical and scientific judgment should be exercised in deciding whether an event is serious because medically significant.

Any suspected transmission via a medicinal product of an infectious agent is also considered a serious adverse reaction.

A **Non-Serious Adverse Event/Non-Serious Adverse Drug Reaction** is an adverse event or adverse drug reaction that does not meet the criteria listed above for a serious adverse event/serious adverse drug reaction.

A **Device Deficiency**, for the purpose of this trial, is any inadequacy of a medical device related to its identity, quality, durability, reliability, safety or performance, such as malfunction.

An **Unanticipated Adverse Device Effect (UADE)** is defined as any serious adverse effect on health or safety or any life-threatening problem or death caused by, or associated with, a device, if that effect, problem, or death was not previously identified in nature, severity, or degree of incidence in the investigational plan or application (including a supplementary plan or application), or any other unanticipated serious problem associated with a device that relates to the rights, safety, or welfare of subjects.

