6.2.3.6 Additional surfactant treatment

Up to two repeated doses could be administered at 100 mg/kg.

A second surfactant dose (poractant alfa 100 mg/kg) will be administered using the same technique as the first dose administration in case of lack of efficacy, or clinical deterioration,

as per randomization criteria ($FiO_2 \geq 0.30$ to maintain preductal oxygen saturation (SpO_2) in the target range 88–95%), within approximately 12 hours from the initial dose.

After the first and the second surfactant administration, neonates could receive a third surfactant dose (poractant alfa 100 mg/kg). If a third dose is administered, it will be provided through a standard technique. Neonates could be intubated (LISA group) or re-intubated (control group) for MV at neonatologist's discretion, if one or more of the below detailed conditions for MV in section 6.2.3.7 are satisfied.

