12.3.5. Safety variables

Adverse Events and Neonatal Morbidities

- Number and percent of neonates reporting AEs started during procedure for surfactant administration as well as AEs started during the procedure and judged related to the procedure will be summarized by treatment group.

For LISA group, any AE assessed as related to CHF 6440 catheter will be considered procedure-related.

These events will be also summarized by treatment group based on action required, if any (i.e. supplementary oxygen or transient increase in FiO₂, manual positive pressure ventilation, endotracheal intubation, administration of, crystalloids, or cardiopulmonary resuscitation or administration of adrenaline). The duration of endotracheal intubation and positive pressure ventilation will be

summarized as well.

A subgroup analysis of AEs during procedure for surfactant administration will be performed based on the use of sedation and/or analgesia (Yes/No).

- Incidence of AEs including neonatal complications of prematurity (see [APPENDIX III](#) for complete list), related AEs (ADRs), serious AEs (SAEs) and AEs leading to death will be summarized by treatment group both in term of frequency of neonates with at least one AE and in term of frequency of AEs (number of events). All the aforementioned categories of AEs will be summarized by System organ Class (SOC) and Preferred Term (PT).
- Frequency of neonates with major neonatal morbidities at discharge or 40 weeks PMA (whichever comes first) will be summarized by treatment group.

Vital Sign

- Vital signs parameters (SBP, DBP MBP, HR and RR) will be summarized as absolute and the change from baseline (pre-procedure) by treatment group using descriptive statistics.

Pain assessment

- PIPP score will be summarized by treatment group by means of descriptive statistics.

First administration

- Number of 1st failed attempt to insert the catheter/ETT will be summarized by treatment group. Percentage of neonates with 1st failed attempt will be compared between group using the Cochran-Mantel-Haenszel adjusted for gestational age group. The CMH adjusted difference with its 95% CI will be presented.
- Number of attempts to the first successful insertion will be summarized by treatment group by means of descriptive statistics.
- Number of device misallocation (i.e., esophageal intubation) will be summarized by treatment group by means of descriptive statistics.

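### The procedural adverse-event variables are not limited to the first dose, and the arm-based procedure window leaves a tube-delivered third dose in the LISA arm undefined

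*Protocol*

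**What the plan says.** - **Number of procedures.** Sections 6.2.2 and 6.2.3.6 allow up to two repeat doses, so a neonate can have one, two or three procedures. Dose 2 uses the technique of dose 1. For dose 3, section 6.2.3.6 says: "If a third dose is administered, it will be provided through a standard technique". It makes no distinction by arm. Elsewhere the protocol uses the word standard for the endotracheal tube method (sections 6.2.3.1 and 6.2.3.4).
- **Variables.** Section 9, like the safety variables in the protocol outline, opens with a block on events during the procedure. Its first item is "Number and percentage of neonates with AEs starting during overall procedure for surfactant administration". Several later items in the block are plain counts of events by action required, some worded in the plural. A separate block headed "After first administration" holds the attempts, misplacements, durations and pain score.
- **Recording and window.** Section 10.8 states: "All AEs during procedures for surfactant administration will be carefully monitored and recorded in both arms". It defines the procedure as running from laryngoscope "up to the removal of the CHF 6440 catheter in the LISA treatment group or the ETT in the comparator arm within one hour" of instillation.
- **Analysis.** Section 12.3.5 summarises "Number and percent of neonates reporting AEs started during procedure for surfactant administration" by treatment group. It adds a sedation/analgesia subgroup but no split by dose number or technique.
- **Single dose.** Section 10.5 describes subjects as receiving one dose of study drug, which does not agree with sections 6.2.2 and 6.2.3.6.

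**The concern.** Adverse events during the procedure come first in the main objective (section 2.1), and section 9 says its variables describe the safety of the two procedures. If the variables cover every dose, two things blur that description.

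First, dose 3 in a LISA-arm neonate is not a LISA procedure, and the arm-based window does not say how to treat it. Second, each re-dosing gives a neonate another chance of an event. Re-dosing is decided open-label and is itself compared between arms (sections 8 and 12.3.4), so the protocol allows for it to differ. A difference in the headline percentage, or its absence, could then partly reflect re-dosing frequency and not risk per procedure. The by-action event counts are more exposed, because they carry no stated denominator in a 2:1 trial.

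**Working it through.** **No figure to reproduce.** The protocol gives no rate for procedural events or re-dosing. Its only number here is the allocation, 100 + 50 = 150 (section 12.1), which is consistent. All rates below are assumptions, with independence between procedures.

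**Reading the window at dose 3**

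| Reading of section 10.8 | LISA arm, tube dose 3 | Control arm, tube dose 3 |
|---|---|---|
| Literal (ends at CHF 6440 removal) | no such catheter in use, so no window | window defined, events count |
| Loose (any dosing procedure) | tube events may enter the LISA figure | events count |

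Unless the variables are limited to dose 1, neither reading gives a LISA-arm figure for LISA procedures on the same footing as the control figure. The as-treated rule in section 12.2 does not help: it covers departures from the randomized treatment, and a protocol-directed tube dose is not one.

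**Effect of unequal re-dosing.** Let p be the risk of at least one event per procedure, equal in both arms, and w the share receiving a second dose.

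P(at least one event) = (1 − w)p + w[1 − (1 − p)²] = p + w·p(1 − p)

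The spurious difference is therefore (w_LISA − w_control)·p(1 − p). With w = 0.30 v 0.15:

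- p = 0.2: 24.8% v 22.4%, +2.4 points
- p = 0.4: 47.2% v 43.6%, +3.6 points
- p = 0.5: 0.15 × 0.25 = +3.75 points (the maximum)
- p = 0.6: 67.2% v 63.6%, +3.6 points

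The sign reverses if controls are re-dosed more, and the difference is zero if the rates are equal.

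A variant lets a quarter of re-dosed neonates go on to dose 3. With dose 2 in 30% or 40% of LISA v 20% of controls and p from 0.2 to 0.6, the difference is +1.9 to +5.5 points. With 20% v 40% it is −3.8 to −5.5. At 40% v 20%, procedures number 100 × (1 + 0.40 + 0.10) = 150 and 50 × (1 + 0.20 + 0.05) = 62.5, that is 1.50 v 1.25 per neonate, a ratio of 1.20.

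**Effect of a tube dose 3 in the LISA arm (loose reading).** Dose 3 follows doses 1 and 2, so it adds a new affected neonate only if both earlier procedures were event-free: share with dose 3 × (1 − q_L)² × q_T, where q_L and q_T are the LISA and tube risks.

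- q_L = 0.30, q_T = 0.60: 0.49 × 0.60 = 0.294 per unit share. At 5% this is 1.5 points, at 10% it is 2.9 points.
- q_L = 0.40, q_T = 0.20 (LISA risk the higher): 0.36 × 0.20 = 0.072 per unit share, or 0.4 to 0.7 points.

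**First dose only.** With equal per-procedure risk, the expected difference between arms is zero whatever the re-dosing rates.

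**The case against.** The best case against is that pooling over doses is nowhere stated. The phrase overall procedure also appears under the first-administration items of section 12.3.5 and, in the outline, for a duration measured once. It may mean one procedure from start to finish. The plural may mean the two techniques. Section 7.1.2 places procedural monitoring in the Day 1 schedule. These points stand to the extent that pooling is an inference from headings and wording. They do not settle the scope. Day 1 runs to 24 hours and dose 2 falls within about 12 hours of dose 1, so Day 1 can hold two procedures.

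A reader might go further and infer that tube events are charged to LISA and that the arms have unequal numbers of procedures. The protocol supports neither as fact. The section 10.8 window is tied to the CHF 6440 catheter, so a tube dose may just as well fall outside it. The re-dosing criterion is the same in both arms, and no rates are given. Nor does re-dosing a control always mean a new intubation, since section 8 foresees controls still intubated after one hour.

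On size, the illustrated shift is small beside sampling error: at 47.2% of 100 v 43.6% of 50, the standard error is √(0.472 × 0.528/100 + 0.436 × 0.564/50) = 8.6 points. Section 1.2 reports some transient events as more frequent with LISA, which favours the smaller dose-3 figures. The variables are only summarised, not tested, and additional doses are reported by arm, so an imbalance would be visible.

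It can also be said that an all-dose percentage by arm validly compares the randomized strategies, re-dosing included. That is true, but only if every dose is counted in both arms, which the literal window prevents. Layout of later-dose tables may properly be left to the statistical analysis plan. The conflict between sections 6.2.3.6, 9, 10.5 and 10.8 is in the protocol itself.

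**Conclusion.** The concern holds as a defect of definition. The protocol does not limit the procedural adverse-event variables to the first administration, does not split them by dose or technique, and defines their window by arm although the third dose uses the standard technique in both. Any all-dose reading treats the arms unequally at dose 3 and lets re-dosing frequency enter the headline percentage.

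On assumed rates the distortion is a few percentage points: +2.4 to +3.75 from 30% v 15% re-dosing, in either direction depending on which arm is re-dosed more and nil if equal, and about 1.5 to 2.9 from a tube dose 3 in 5% to 10% of LISA neonates at 30% LISA and 60% tube risk. Unequal re-dosing is generally the larger effect. The protocol does not show that a bias against LISA will occur. The change should be made because the variable leads the main objective and the correction is cheap.

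**What to change.** - In sections 9 and 12.3.5, and in the matching outline text, base the by-arm procedural adverse-event variables (all, procedure-related, by action required) on the first-dose procedure.
- Tabulate events of dose 2 and dose 3 procedures separately, by the technique actually used, with the number of procedures as denominator.
- In section 10.8, define the start and end of the window by the device used for that dose instead of by arm.
- Reconcile the single-dose statement in section 10.5 with sections 6.2.2 and 6.2.3.6.

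The cost is wording and one extra table. Events at doses 2 and 3 leave the headline count but stay reported. No change to dosing or to the technique for any dose is proposed.
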